## 10.4.4.4. Treatment Compliance

Study treatment compliance will be assessed by treatment group using the following parameter:

• The injection frequency will be defined for each patient as the average number of days between 2 injections, that is: (last dose date minus first dose date)/(number of injections minus 1)

These parameters will be summarized descriptively (N, mean, standard deviation, median, minimum and maximum).

### 10.4.5. Other Endpoints

The other endpoints described in Section 4.2.3 will be summarized descriptively by the randomized treatment group in the neurocognitive function study (R727-CL-1532).

# **10.5.** Additional Statistical Data Handling Conventions

The following analysis and data conventions will be followed:

Definition of baseline:

- The last available value before the first dose in the neurocognitive function study, R727-CL-1532.
- In addition to the OLE study database, some data will be recovered from the neurocognitive function study (R727-CL-1532) database

**Regeneron Pharmaceuticals, Inc.** 

### CONFIDENTIAL

General rules for handling missing data:

- If the start date of an AE or concomitant medication is incomplete or missing, it will be assumed to have occurred on or after the intake of study medication, except if an incomplete date (eg, month and year) clearly indicates that the event started prior to treatment. If the partial date indicates the same month or year of the intake of study medication date, then the start date by the study medication intake date will be imputed; otherwise, the missing day or month by the first day or the first month will be imputed.
- No imputations for missing safety data will be made.

Visit windows:

• Assessments taken outside of the analysis windows specified in the SAP will be displayed according to the case report form (CRF) assessment recorded by the investigator.

Unscheduled assessments:

- Extra assessments (laboratory safety data or vital signs associated with nonprotocol clinical visits or obtained in the course of investigating or managing AEs) will be summarized based on the analysis windows specified in the SAP. If more than 1 laboratory value is available for a given visit, the first observation will be used in summaries and all observations will be presented in listings.
- Extra assessment (laboratory safety data or vital signs associated with nonprotocol clinical visits or obtained in the course of investigating or managing AEs) will also be used in PCSA analyses if within the TEAE period.

# **10.6.** Statistical Considerations Surrounding the Premature Termination of a Study

If the study is terminated prematurely, only those parameters required for the development program and/or reporting to regulatory authorities will be summarized. Investigator and sponsor responsibilities surrounding the premature termination of a study are presented in Section 16.1.

# 11. DATA MANAGEMENT AND ELECTRONIC SYSTEMS

### 11.1. Data Management

A data management plan specifying all relevant aspects of data processing for the study (including data validation, cleaning, correcting, releasing) will be maintained and stored at Regeneron.

A medical coding plan will specify the processes and the dictionary used for coding. All data coding (eg, AEs, baseline findings, medication, medical history/surgical history) will be done using internationally recognized and accepted dictionaries.

The CRF data for this study will be collected with an EDC tool.

**Regeneron Pharmaceuticals, Inc.** 

CONFIDENTIAL

Page 46 of 57

# **11.2.** Electronic Systems

Electronic systems that may be used to process and/or collect data in this study will include the following:

- IVRS/IWRS system –management of study drug supply
- EDC system data capture
- Statistical Analysis System (SAS) statistical review and analysis
- AWARE, Business Objects XI pharmacovigilance activities

# **12.** STUDY MONITORING

# 12.1. Monitoring of Study Sites

The study monitor and/or designee (eg, CRO monitor) will visit each site following enrollment of the first patient, and periodically during the study. In accordance with ICH guidelines, the monitor will compare the CRF entries with the appropriate source documents. Additional review may include, but is not limited to, patient ICFs, documentation of patient recruitment and follow-up, AEs, SAEs, and concomitant therapy; as well as records of study drug dispensing, compliance, and accountability. A copy of the drug dispensing log must be provided to the sponsor upon request.

# 12.2. Source Document Requirements

Investigators are required to prepare and maintain adequate and accurate patient records (source documents).

The investigator must keep all source documents on file with the CRF (throughout this protocol, CRF refers to either a paper CRF or an electronic CRF). Case report forms and source documents must be available at all times for inspection by authorized representatives of the sponsor and regulatory authorities.

# **12.3.** Case Report Form Requirements

Study data obtained in the course of the clinical study will be recorded on CRFs by trained site personnel. A CRF must be completed for every patient enrolled in the study. After review of the clinical data for each patient, the investigator must provide an electronic signature. A copy of each CRF page is to be retained by the investigator as part of the study record and must be available at all times for inspection by authorized representatives of the sponsor and regulatory authorities.

Corrections to the CRF will be entered in the CRF by the investigator or an authorized designee. All changes, including date and person performing the corrections, will be available via a systemgenerated audit trail. For corrections made via data queries, a reason for any alteration must be provided.

**Regeneron Pharmaceuticals, Inc.** 

# **13.** AUDITS AND INSPECTIONS

This study may be subject to a quality assurance audit or inspection by the sponsor or regulatory authorities. Should this occur, the investigator is responsible for:

- Informing the sponsor of a planned inspection by the authorities as soon as notification is received, and authorizing the sponsor's participation in the inspection
- Providing access to all necessary facilities, study data, and documents for the inspection or audit
- Communicating any information arising from inspection by the regulatory authorities to the sponsor immediately
- Taking all appropriate measures requested by the sponsor to resolve the problems found during the audit or inspection

Documents subject to audit or inspection include but are not limited to all source documents, CRFs, medical records, correspondence, ICFs, IRB/EC files, documentation of certification and quality control of supporting laboratories, and records relevant to the study maintained in any supporting pharmacy facilities. Conditions of study material storage are also subject to inspection. In addition, representatives of the sponsor may observe the conduct of any aspect of the clinical study or its supporting activities both within and outside of the investigator's institution.

In all instances, the confidentiality of the data must be respected.

# 14. ETHICAL AND REGULATORY CONSIDERATIONS

# 14.1. Good Clinical Practice Statement

It is the responsibility of both the sponsor and the investigator(s) to ensure that this clinical study will be conducted in accordance with the ethical principles that have their origin in the Declaration of Helsinki, and that are consistent with the International Council for Harmonisation (ICH) guidelines for GCP and applicable regulatory requirements.

# 14.2. Informed Consent

The principles of informed consent are described in ICH guidelines for GCP.

The ICF used by the investigator must be reviewed and approved by the sponsor prior to submission to the appropriate IRB/EC. A copy of the IRB/EC-approved ICF and documentation of approval must be provided to the sponsor before study drug will be shipped to the study site.

It is the responsibility of the investigator or designee (if acceptable by local regulations) to obtain written informed consent from each patient prior to his/her participation in the study and after the aims, methods, objectives, and potential hazards of the study have been explained to the patient in language that he/she can understand. The ICF should be signed and dated by the patient and by the investigator or authorized designee who reviewed the ICF with the patient.

• Patients who can write but cannot read will have the ICF read to them before signing and dating the ICF.

• Patients who can understand but who can neither write nor read will have the ICF read to them in presence of an impartial witness, who will sign and date the ICF to confirm that informed consent was given.

The original ICF must be retained by the investigator as part of the patient's study record, and a copy of the signed ICF must be given to the patient.

If new safety information results in significant changes in the risk/benefit assessment, the ICF must be reviewed and updated appropriately. All study patients must be informed of the new information and provide their written consent if they wish to continue in the study. The original signed revised ICF must be maintained in the patient's study record and a copy must be given to the patient.

## 14.3. Patient Confidentiality and Data Protection

The investigator must take all appropriate measures to ensure that the anonymity of each study patient will be maintained. Patients should be identified by their initials and a patient identification number, only, on CRFs or other documents submitted to the sponsor. Documents that will not be submitted to the sponsor (eg, signed ICF) must be kept in strict confidence.

The patient's and investigator's personal data, which may be included in the sponsor database, will be treated in compliance with all applicable laws and regulations. The sponsor shall take all appropriate measures to safeguard and prevent access to this data by any unauthorized third party.

## 14.4. Institutional Review Board/Ethics Committee

An appropriately constituted IRB/EC, as described in ICH guidelines for GCP, must review and approve:

- The protocol, ICF, and any other materials to be provided to the patients (eg, advertising) before any patient may be enrolled in the study
- Any amendment or modification to the study protocol or ICF before implementation, unless the change is necessary to eliminate an immediate hazard to the patients, in which case the IRB/EC should be informed as soon as possible
- Ongoing studies on an annual basis or at intervals appropriate to the degree of risk

In addition, the IRB/EC should be informed of any event likely to affect the safety of patients or the continued conduct of the clinical study.

A copy of the IRB/EC approval letter with a current list of the IRB/EC members and their functions must be received by the sponsor prior to shipment of drug supplies to the investigator. The approval letter should include the study number and title, the documents reviewed, and the date of the review.

Records of the IRB/EC review and approval of all study documents (including approval of ongoing studies) must be kept on file by the investigator.

## **15. PROTOCOL AMENDMENTS**

The sponsor may not implement a change in the design of the protocol or ICF without an IRB/EC-approved amendment

# 16. PREMATURE TERMINATION OF THE STUDY OR CLOSE-OUT OF A SITE

## **16.1. Premature Termination of the Study**

The sponsor has the right to terminate the study prematurely. Reasons may include efficacy, safety, or futility, among others. Should the sponsor decide to terminate the study, the investigator(s) will be notified in writing.

## 16.2. Close-out of a Site

The sponsor and the investigator have the right to close-out a site prematurely.

### Investigator's Decision

The investigator must notify the sponsor of a desire to close-out a site in writing, providing at least 30 days' notice. The final decision should be made through mutual agreement with the sponsor. Both parties will arrange the close-out procedures after review and consultation.

### Sponsor's Decision

The sponsor will notify the investigator(s) of a decision to close-out a study site in writing. Reasons may include the following, among others:

- The investigator has received all items and information necessary to perform the study, but has not enrolled any patient within a reasonable period of time
- The investigator has violated any fundamental obligation in the study agreement, including but not limited to, breach of this protocol (and any applicable amendments), breach of the applicable laws and regulations, or breach of any applicable ICH guidelines
- The total number of patients required for the study are enrolled earlier than expected

In all cases, the appropriate IRB/EC and Health Authorities must be informed according to applicable regulatory requirements, and adequate consideration must be given to the protection of the patients' interests.

# **17. STUDY DOCUMENTATION**

## 17.1. Certification of Accuracy of Data

A declaration assuring the accuracy and content of the data recorded on the CRF must be signed electronically by the investigator. This signed declaration accompanies each set of patient final CRF that will be provided to the sponsor.

## **17.2.** Retention of Records

The investigator must retain all essential study documents, including ICFs, source documents, investigator copies of CRFs, and drug accountability records for at least 15 years following the completion or discontinuation of the study, or longer, if a longer period is required by relevant regulatory authorities. The investigator must consult with the sponsor before discarding or destroying any essential study documents following study completion or discontinuation. Records must be destroyed in a manner that ensures confidentiality.

If the investigator's personal situation is such that archiving can no longer be ensured, the investigator must inform the sponsor and the relevant records will be transferred to a mutually agreed-upon destination.

# **18. DATA QUALITY ASSURANCE**

In accordance with ICH E6, the sponsor is responsible for quality assurance to ensure that the study is conducted and the data generated, recorded, and reported in compliance with the protocol, GCP, and any applicable regulatory requirement(s). The planned quality assurance and quality control procedures for the study are summarized.

### Data Management

The sponsor is responsible for the data management of this study including quality checking of the data (Section 11.1).

### Study Monitoring

The investigator must allow study-related monitoring, IRB/EC review, audits, and inspections from relevant health regulatory authorities, and provide direct access to source data documents (Section 12.1, Section 12.2, and Section 13).

The study monitors will perform ongoing source data review to verify that data recorded in the CRF by authorized site personnel are accurate, complete, and verifiable from source documents, that the safety and rights of patients are being protected, and that the study is being conducted in accordance with the current approved protocol version and any other study agreements, ICH GCP, and all applicable regulatory requirements (Section 12.1).

All subject/patient data collected during the study will be recorded on paper or electronic CRF unless the data are transmitted to the sponsor or designee electronically (eg, laboratory data). The investigator is responsible for affirming that data entries in the CRF are accurate and correct by electronically signing a declaration that accompanies each set of patient/subject final CRF (Section 12.3 and Section 17.1).

### Study Documentation

The investigator must maintain accurate documentation (source data) that supports the information entered in the CRF (Section 12.3).

The investigator will retain all records and documents, including signed ICFs, pertaining to the conduct of this study for at least 15 years after study completion, unless local regulations or institutional policies require a longer retention period. No records may be destroyed during the retention period without the written approval of the sponsor. No records may be transferred to another location or party without written notification to the sponsor (Section 17.2).

## **19. CONFIDENTIALITY**

Confidentiality of information is provided as a separate agreement.

## **20.** FINANCING AND INSURANCE

Financing and insurance information is provided as a separate agreement.

# 21. PUBLICATION POLICY

The publication policy is provided as a separate agreement.

## APPENDIX 1. FACTORS TO CONSIDER IN ASSESSING THE RELATIONSHIP OF ADVERSE EVENTS TO STUDY DRUG AND STUDY CONDUCT

Is there a reasonable possibility that the event may have been caused by the study drug or study conduct?

No:

- due to external causes such as environmental factors or other treatment(s) being administered
- due to the patient's disease state or clinical condition
- do not follow a reasonable temporal sequence following the time of administration of the dose of study drug
- do not reappear or worsen when dosing with study drug is resumed
- are not a suspected response to the study drug based upon preclinical data or prior clinical data

Yes:

- could not be explained by environmental factors or other treatment(s) being administered
- could not be explained by the patient's disease state or clinical condition
- follow a reasonable temporal sequence following the time of administration of the dose of study drug
- resolve or improve after discontinuation of study drug
- reappear or worsen when dosing with study drug is resumed
- are known or suspected to be a response to the study drug based upon preclinical data or prior clinical data

NOTE: This list is not exhaustive.

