## 9.2. Obligations of Sponsor

During the course of the study, the sponsor will report in an expedited manner all SAEs that are both unexpected and at least reasonably related to the study drug (suspected unexpected serious adverse reaction [SUSAR]), to the health authorities, ECs/IRBs as appropriate, and to the investigators.

In addition, the sponsor will report in an expedited manner all SAEs that are expected and at least reasonably related to the study drug to the health authorities, according to local regulations.

At the completion of the study, the sponsor will report all safety observations made during the conduct of the trial in the clinical study report to health authorities and ECs/IRB as appropriate.

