**Regeneron Pharmaceuticals, Inc.** 

### CONFIDENTIAL

Page 37 of 57

obtain follow-up information on the outcome until the event is considered chronic and/or stable.

• SAE with an onset day greater than 30 days from the end of study/early termination visit - only fatal SAEs and those deemed by the investigator to be drug-related SAEs will be reported to the sponsor. The investigator should make every effort to obtain follow-up information on the outcome of a drug-related SAE until the event is considered chronic and/or stable.

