### 9.5.2. Evaluation of Causality

### **Relationship of Adverse Events to Study Drug:**

The relationship of AEs to study drug will be assessed by the investigator, and will be a clinical decision based on all available information. The following question will be addressed:

Is there a reasonable possibility that the AE may have been caused by the study drug?

The possible answers are:

- **Not Related:** There is no reasonable possibility that the event may have been caused by the study drug
- **Related:** There is a reasonable possibility that the event may have been caused by the study drug

A list of factors to consider when assessing the relationship of AEs to study drug is provided in Appendix 1.

The investigator should justify the causality assessment of each SAE.

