### Not Related:

- Existence of a clear alternative explanation or nonplausibility (eg, the patient is struck by an automobile when there is no indication that the drug caused disorientation, or cancer diagnosed a few days after first drug administration)
- Due to external causes such as other treatment(s) being administered
- Due to the patient's disease state or clinical condition
- Does not follow a reasonable temporal sequence following the time of administration of the dose of study drug
- Does not reappear or worsen when dosing with study drug is resumed (ie, negative re-challenge)

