### **Related:**

- Could not be explained by other treatment(s) being administered
- Could not be explained by the patient's disease state or clinical condition
- Follows a reasonable temporal sequence following the time of administration of the dose of study drug
- Resolves or improves after discontinuation of study drug
- Reappears or worsens when dosing with study drug is resumed (ie, positive re-challenge)
- Known to be a response to the study drug based upon preclinical data or prior clinical data
- Known to be strongly associated with drug exposure (eg, angioedema, Stevens-Johnson Syndrome)

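### Appendix 1 counts the absence of prior suspicion against drug causality, while section 9.5.2, which sends investigators there, does not

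*Protocol*

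**What the plan says.** Protocol section 9.5.2 asks the investigator whether there is a reasonable possibility that the drug caused the event, with two possible answers, related or not related. It states that the assessment "will be a clinical decision based on all available information" and adds: "A list of factors to consider when assessing the relationship of AEs to study drug is provided in Appendix 1". It then gives its own lists of factors for each answer.

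Appendix 1 puts much the same question, widened to study conduct, and lists factors under 'No' and 'Yes'. The last factor under 'No' is that events "are not a suspected response to the study drug based upon preclinical data or prior clinical data". The appendix closes with "NOTE: This list is not exhaustive".

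In section 9.5.2, prior knowledge appears only under 'Related', as "Known to be a response to the study drug based upon preclinical data or prior clinical data". Its 'Not Related' list does not mention prior knowledge.

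**The concern.** An investigator who follows the protocol reads both lists, and they disagree about an event with no precedent. Section 9.5.2 treats the lack of a precedent as neutral. Appendix 1 treats it as evidence against the drug.

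This matters because the primary objective is long-term safety. The study has no control arm, so the judgement on an individual case carries more weight than it would in a randomised comparison. Section 9.2 reserves expedited SUSAR reporting for "all SAEs that are both unexpected and at least reasonably related to the study drug". A factor that counts novelty against relatedness pulls against the second half of that test in just the cases where the first half is likely to be met. The SAP leans the other way in its own default: section 6.3 counts an event with a missing causality assessment as possibly related.

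**Working it through.** No arithmetic applies, because the plan gives no figure on this point. The check compares the two current lists and then traces where the related/not-related answer is used.

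**Step 1. Compare the factors against causality.**

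| Factor against causality | Section 9.5.2, 'Not Related' | Appendix 1, 'No' |
|---|---|---|
| Clear alternative explanation or implausibility | yes | no |
| External causes, such as other treatments | yes | yes (also environmental factors) |
| Disease or clinical condition | yes | yes |
| Timing does not fit | yes | yes |
| Negative re-challenge | yes | yes |
| No prior suspicion from preclinical or clinical data | **no** | **yes** |

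Each list has five factors and four are common to both. The factor at issue is the only one that Appendix 1 has and section 9.5.2 lacks.

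**Step 2. Compare the factors for causality.** Section 9.5.2 has seven and Appendix 1 has six. The six correspond, apart from small differences in wording: Appendix 1 again adds environmental factors, and its prior-knowledge factor covers suspected as well as known responses. Section 9.5.2 also lists events strongly associated with drug exposure. So both lists let prior knowledge count for the drug, but only Appendix 1 lets its absence count against.

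**Step 3. Apply both lists to one hypothetical event.** Take an event with plausible timing, not explained by other treatment or by disease, which resolves after the drug is stopped. The drug is not restarted, and nothing in earlier data suggested the event.
- Section 9.5.2: four factors for, none against.
- Appendix 1: the same four for, one against.

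The factors are not scored, so this does not decide the answer. It shows that the same facts look less drug-related under Appendix 1, solely because the event is new.

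**Step 4. Trace the answer.**

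| Output | Depends on causality? | Where |
|---|---|---|
| SUSAR classification and investigator alerts | yes | Protocol 9.2, 9.7 |
| Required IRB/EC reporting of non-fatal SAEs as drug-related | yes | Protocol 9.1 |
| Non-fatal SAEs starting more than 30 days after the last visit | yes | Protocol 9.4.2 |
| Tables of related TEAEs and related serious TEAEs | yes | Protocol 10.4.4.1; SAP 5.7.1 |
| AE collection | no | Protocol 9.4.1 |
| 24-hour reporting of other SAEs to the sponsor | no | Protocol 9.4.2 |
| 24-hour reporting of AESIs | no | Protocol 9.4.3 |
| Primary endpoint, AE incidence | no | Protocol 4.2.1; SAP 4.6.1 |

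The late-SAE route is the only one where the event itself can be lost. Beyond 30 days after the last visit, "only fatal SAEs and those deemed by the investigator to be drug-related SAEs will be reported to the sponsor". A late, non-fatal SAE judged unrelated because it was new would therefore not reach the sponsor. In the other causality-dependent routes the event is in the database and only its classification or onward reporting is at risk.

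**The case against.** The strongest reply is that Appendix 1 does not direct an answer. A reader might infer that any event not previously suspected must be coded unrelated. The documents do not support that: the appendix offers factors to consider, says its list is incomplete, and sits under a section that calls for an overall clinical judgement. A new event can satisfy several 'Yes' factors at once. This stands, and it limits the point to a bias in judgement.

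A reader might also infer that the factor catches every possible SUSAR. It does not. Section 9.7 defines unexpected by reference to the Investigator's Brochure or the protocol, whereas the Appendix 1 factor turns on suspicion from preclinical or clinical data. The two tests overlap, but an event can be suspected and still unexpected. Section 9.2 also does not say whose causality assessment governs, so the effect on SUSAR reporting is possible rather than certain.

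Nor do the documents support saying that safety detection as a whole is suppressed. Step 4 shows that the main routes do not depend on causality. In addition, section 9.1 recommends sending all SAEs to the IRB/EC, section 9.6 has the sponsor review individual SAEs and cumulative data, and an independent committee adjudicates neurocognitive events and whether a possible etiology is identified (SAP 4.7.1.2). These safeguards are real. However, none of these passages provides for a sponsor causality assessment that would correct the investigator's answer.

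Two further extensions fail. Restarting the drug after a temporary stop (Protocol 7.3.2.2) rests on the investigator's medical judgement and does not cite Appendix 1. The amendment history records a deletion from section 9.5.2 of a related statement about known responses. The current section 9.5.2 is consistent with that entry, so the log shows no separate error. The point rests on the two current texts alone.

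**Conclusion.** The point holds as an inconsistency between two current, cross-referenced lists, and its direction is clear: for events with no precedent, Appendix 1 leans towards 'not related' and section 9.5.2 does not. Its reach is the four causality-dependent outputs in Step 4, and outright loss is confined to late, non-fatal, post-study SAEs. Those also start after the TEAE period, which ends at the last visit (Protocol 10.4.4.1; SAP 4.7.1), so they would not alter the TEAE tables.

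No numerical size can be given. The documents do not say how often investigators rely on this factor or how many new events to expect, and any assumed share would simply come back as the answer. The conclusion assumes that investigators do consult Appendix 1, as section 9.5.2 tells them to.

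This should be fixed, but it does not threaten the primary analysis. The early termination on January 31, 2020 (SAP 1.1) reduces the benefit for future assessments. What remains is the classification of events already recorded and any late SAE reports.

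**What to change.** 1. Delete the factor on absence of prior suspicion from the 'No' list in Appendix 1. Keep its counterpart under 'Yes'.
2. Reconcile the rest, so that investigators have one list. Deleting the bullet alone does not make the two match: Appendix 1 would still lack the alternative-explanation factor and the factor for events strongly associated with drug exposure, and would still add environmental factors and study conduct. Keeping a single list and pointing to it from the other place would be simplest.
3. Make the change through an IRB/EC-approved amendment where section 15 of the protocol requires one, and tell sites which list applies.
4. Before the related-event tables are finalised, identify SAEs whose recorded justification for 'not related' rests on this factor alone, and ask the investigator to reassess them. Section 9.5.2 says investigators should justify causality for each SAE, so this is feasible for SAEs. It makes no such request for non-serious events, so the check cannot extend to them in the same way.

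The text change is small. The main cost is the amendment, where needed, and the review of SAE justifications. The downside is that a few more events may be classed as related. No dose, visit or treatment rule changes.
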